### 3) Medical History and Concurrent Disease

- a) Prior malignancy active within the previous 3 years except for locally curable cancers that have been apparently cured, [REDACTED].
  - i) In Part 2, the BMS-986288 Cohort Initial Expansion Phase, participants with concurrent malignancies that do not require treatment and are clinically stable and anticipated to be followed in an active surveillance manner for the next 12 months are eligible. Treatment should not be required at timing of consent and not be expected to be needed not only for the concurrent malignancy, but also for complications caused by it. The Investigator should inform the participant that the study treatment is not intended and not expected to be considered as treatment for the concurrent malignancy.
- b) Participants with other active malignancy requiring concurrent intervention.
- c) Prior organ allograft.

- d) Toxicity (except for alopecia) related to prior anti-cancer therapy and/or surgery, unless the toxicity is resolved, returned to baseline or Grade 1, or deemed irreversible.
  - i) Any active neuropathy > Grade 2 (National Cancer Institute [NCI] Common Terminology Criteria for Adverse Events [CTCAE] v5.0).
- e) Participants with the following:
  - i) Active, known, or suspected autoimmune disease, including history of uveitis or autoimmune ocular disease.
    - (1) Participants with well-controlled asthma and/or mild allergic rhinitis (seasonal allergies) are eligible.
    - (2) Participants with the following disease conditions are also eligible:
      - (a) Vitiligo.
      - (b) Type 1 diabetes mellitus.
      - (c) Residual hypothyroidism due to autoimmune condition only requiring hormone replacement.
      - (d) Euthyroid participants with a history of Grave's disease (participants with suspected autoimmune thyroid disorders must be negative for thyroglobulin and thyroid peroxidase antibodies and thyroid stimulating Ig prior to the first dose of study treatment).
      - (e) Psoriasis not requiring systemic treatment or conditions not expected to recur in the absence of an external trigger are permitted to enroll.
  - ii) History of life-threatening toxicity related to prior immune therapy or any toxicity that resulted in permanent discontinuation from prior immune therapy (eg, anti-CTLA-4 or anti-PD-(L)1 treatment or any other antibody or drug specifically targeting [REDACTED] co-stimulation or immune-checkpoint pathways) except those that are unlikely to re-occur with standard countermeasures (eg, hormone replacement after adrenal crisis).
  - iii) Conditions requiring systemic treatment with corticosteroids > 10 mg daily prednisone equivalent within 14 days or other immunosuppressive medications within 30 days of study treatment administration. Inhaled or topical steroids and adrenal replacement steroid doses of  $\geq$ 10 mg daily prednisone equivalent are permitted in the absence of active autoimmune disease.
    - (1) Treatment with a short course of steroids (< 5 days) up to 7 days prior to initiating study treatment is permitted.
  - iv) Uncontrolled or significant cardiovascular disease including, but not limited, to any of the following:
    - (1) Myocardial infarction or stroke/transient ischemic attack within the past 6 months.
    - (2) Uncontrolled angina within the past 3 months.
    - (3) Any history of clinically significant arrhythmias (such as ventricular tachycardia, ventricular fibrillation, or torsades de pointes).
    - (4) **Not Applicable as of Amendment 03. See 3.e.iv.9 below:** History of other clinically significant heart disease (eg, cardiomyopathy, congestive heart failure with New York Heart Association functional classification III to IV [Appendix 10], pericarditis, or significant pericardial effusion).

- (5) History of myocarditis, regardless of etiology.
- (6) Cardiovascular disease-related requirement for daily supplemental oxygen therapy.
- (7) QT interval corrected for heart rate using Fridericia's formula (QTcF) prolongation > 480 msec, except for right bundle branch block.
- (8) History of other clinically significant heart disease (eg, cardiomyopathy, congestive heart failure with New York Heart Association functional classification II, III, or IV [[Appendix 10](#)], pericarditis, or significant pericardial effusion).
- v) **Not Applicable as of Amendment 02. See 3.e.xiii and xiv below:** History of chronic hepatitis as evidenced by the following:
  - (1) Positive test for hepatitis B surface antigen (HBsAg).
  - (2) Positive test for qualitative hepatitis C viral load by polymerase chain reaction (PCR).
    - (a) Participants with positive hepatitis C antibody and negative quantitative hepatitis C by PCR are eligible. History of resolved hepatitis A virus infection is not an exclusion criterion.
    - (b) Additional testing or substitute testing per institutional guidelines to rule out infection is permitted.
- vi) Evidence of active infection that requires systemic antibacterial, antiviral, or antifungal therapy ≤ 7 days prior to the first dose of study treatment (except for viral infections that are presumed to be associated with the underlying tumor type required for study entry).
- vii) Any major surgery within 4 weeks of the first dose of study treatment. Participants must have recovered from the effects of major surgery or significant traumatic injury at least 14 days before the first dose of study treatment.
- viii) Receipt of packed red blood cells or platelet transfusion within 2 weeks of the first dose of study treatment.
- ix) Any known or underlying medical, psychiatric condition and/or social reason that, in the opinion of the Investigator or Sponsor, could make the administration of study treatment hazardous to the participants or could adversely affect the ability of the participant to comply with or tolerate the study.
- x) **Not Applicable as of Amendment 02. See 3.e.xv below:** Positive test for human immunodeficiency virus (HIV).

Note: Testing for HIV must be performed at sites where mandated by local requirements.
- xi) Interstitial lung disease that is symptomatic or may interfere with the detection or management of suspected treatment-related pulmonary toxicity.
- xii) WOCBP who are pregnant or breastfeeding.
- xiii) Any positive test result for hepatitis B virus (HBV) indicating presence of virus, eg, HBsAg, Australia antigen positive.
- xiv) Any positive test result for hepatitis C virus (HCV) indicating presence of active viral replication (detectable HCV-RNA). Note: Participants with positive HCV antibody and an undetectable HCV RNA are eligible to enroll.

xv) Known human immunodeficiency virus (HIV) positive with an AIDS-defining opportunistic infection within the last year, or a current CD4 count < 350 cells/uL.

Participants with HIV are eligible if:

a) they have received antiretroviral therapy (ART) for at least 4 weeks prior to treatment assignment, as clinically indicated, while enrolled on study

b) they continue on ART as clinically indicated while enrolled on study

c) CD4 counts and viral load are monitored per standard of care by a local health care provider.

NOTE: Testing for HIV must be performed at sites where mandated locally. HIV-positive participants must be excluded where mandated locally.

xvi) Participants with serious or uncontrolled medical disorders.

xvii) Participant has any condition, including active or uncontrolled infection, or the presence of laboratory abnormalities, which places the participant at unacceptable risk if he/she were to participate in the study.

xviii) Previous SARS-CoV-2 infection within 10 days for mild or asymptomatic infections or 20 days for severe/critical illness prior to screening or predose C1D1.

(1) Acute symptoms must have resolved and based on investigator assessment in consultation with the medical monitor, there are no sequelae that would place the participant at a higher risk of receiving study treatment.

xix) For MSS CRC Part 2C

(1) Any evidence of active bleeding, or hemorrhage or bleeding event  $\geq$  NCI-CTCAE version 5.0 Grade 3 within 4 weeks prior to the start of study medication.

(2) Arterial or venous thrombotic or embolic events such as cerebrovascular accident (including transient ischemic attacks), deep vein thrombosis, or pulmonary embolism within 6 months before the start of study medication (except for adequately treated catheter-related venous thrombosis occurring more than 1 month before the start of study medication).

(3) Prior or current gastrointestinal perforation or fistula.

(4) Non-healing wound, non-healing ulcer, or non-healing bone fracture.

#### **4) Allergies and Adverse Drug Reactions**

a) History of allergy to study treatment(s) or any of its components.

b) History of severe hypersensitivity reaction to any mAb.

#### **5) Other Exclusion Criteria**

a) Prisoners or participants who are involuntarily incarcerated. (Note: Under certain specific circumstances, and only in countries where local regulations permit, a person who has been imprisoned may be included or permitted to continue as a participant. Strict conditions apply, and BMS approval is required.)

b) Participants who are compulsorily detained for treatment of either a psychiatric or a physical (eg, infectious disease) illness.

Eligibility criteria for this study have been carefully considered to ensure the safety of the study participants and that the results of the study can be used. It is imperative that participants fully meet all eligibility criteria.

### **6.3 Lifestyle Restrictions**

Not applicable. No restrictions are required.

### **6.4 Screen Failures**

Screen failures are defined as participants who consent to participate in the clinical study but who are not subsequently entered in the study/included in the analysis population. A minimal set of screen failure information is required to ensure transparent reporting of screen failure participants, to meet the Consolidated Standards of Reporting Trials (CONSORT) publishing requirements, as applicable, and to respond to queries from regulatory authorities. Minimal information includes date of consent, demography, screen failure details, eligibility criteria, and any serious AEs.

#### **6.4.1 Retesting During Screening or Lead-In Period**

This study permits the re-enrollment of a participant who has discontinued the study as a pretreatment failure (ie, participant has not been treated).

Retesting of laboratory parameters and/or other assessments during the extended screening period will be allowed. The most current result prior to treatment allocation is the value by which study inclusion will be assessed, as it represents the participant's most current clinical state.

Laboratory parameters and/or assessments that are included in [Table 2-1](#) may be repeated in an effort to find all possible well qualified participants. Consultation with the Medical Monitor (or designee) may be needed to identify whether repeat testing of any particular parameter is clinically relevant.

- Testing for asymptomatic SARS-CoV-2 infection by reverse transcription polymerase chain reaction (RT-PCR) or viral antigen is not required. However, some participants may develop suspected or confirmed symptomatic SARS-CoV-2 infection or be discovered to have asymptomatic SARS-CoV-2 infection during the screening period. In such cases, participants may be considered eligible for the study after meeting all inclusion/exclusion criteria related to active infection, and after meeting the following criteria:
  - At least 10 days (20 days for severe/critical illness) have passed since symptoms first appeared or positive RT-PCR or viral antigen test result, and
  - At least 24 hours have passed since last fever without the use of fever-reducing medications, and
  - Acute symptoms (eg, cough, shortness of breath) have resolved and
  - In the opinion of the investigator, there are no SARS-CoV-2 infection sequelae that may place the participant at a higher risk of receiving investigational treatment
- In the instance of a SARS-CoV-2 infection during screening, the screening period may be extended beyond the protocol-specified timeframe with medical monitor approval. Any screening tests already performed which could potentially be affected by the SARS-CoV-2

infection or its complications on an individual basis and agreed upon with the Medical Monitor (eg, safety labs, oxygen saturation, chest CT scan) should be repeated.

## 7 TREATMENTS ADMINISTERED

Study treatment is defined as any investigational treatment(s), marketed product(s), placebo or medical device intended to be administered to a study participant according to the study treatment allocation.

An investigational product (IP), also known as investigational medicinal product (IMP) in some regions, is defined as a pharmaceutical form of an active substance or placebo being tested or used as a reference in a clinical study, including products already with a marketing authorization but used or assembled (formulated or packaged) differently than the authorized form, or used for an unauthorized indication, or when used to gain further information about the authorized form.

Other medications used as support or escape medication for preventative, diagnostic, or therapeutic reasons, as components of the standard of care for a given diagnosis, may be considered non-IPs.

In this protocol, IPs are the following:

- BMS-986288
- Nivolumab
- [REDACTED]
- Regorafenib

All 4 drugs used in this open-label study qualify as IPs, as per previous text, and their description and storage information are shown in [Table 7-1](#).

**Table 7-1: Investigational Product Description for CA043001**

Product Description / Class and Dosage Form	Potency	IP/Non-IP	Blinded or Open Label	Packaging / Appearance	Storage Conditions (per label)
Nivolumab (BMS-936558) Solution for Injection	█ mg (10 mg/mL)	IP	Open label	Vial	Refer to the label on container and/or Pharmacy Manual
BMS-986288 Powder for Solution for Injection	█ mg per vial	IP	Open label	Vial	Refer to the label on container and/or Pharmacy Manual
██████████	█ mg (1 mg/mL)	IP	Open label	Vial	Refer to the label on container and/or Pharmacy Manual
Regorafenib Tablet b	40 mg c	IP	Open Label	Bottle	Refer to the label on container and/or Pharmacy Manual

Abbreviations: IP = investigational product; ██████████ ██████████ ██████████

b These products may be obtained by investigational sites as local commercial product in certain countries if allowed by local regulations. In these cases, products may be a different pack size/potency than listed in the table. These products should be prepared/stored/administered in accordance with the package insert or SmPC.

c May include other commercially available strengths.

## 7.1 Schedule of Dose for Each Investigational Product

The dosing schedule for each IP is detailed below in Table 7.1-1 for all study parts. Planned dose levels may be modified (eg, change in administration schedule) or intermediate dose levels may be added, based upon the BLRM analysis and clinical evaluation of available safety, PK, and pharmacodynamic data.

All participants will be monitored continuously for AEs while on study treatment. Treatment modifications (eg, dose delay or discontinuation) will be based on specific laboratory and AE criteria, as described in [Section 7.4](#).

**Table 7.1-1: Selection and Timing of Dosea**

Study Treatment	Planned Unit Dose Strength(s)/ Dosage Level(s)	Planned Dosage Formulation Frequency of Administration	Route of Administration
BMS-986288	[REDACTED] [REDACTED], and [REDACTED] mg	[REDACTED]	IV
Nivolumab	[REDACTED] mg	[REDACTED]	IV
BMS-986288/ Nivolumab	[REDACTED] mg a / [REDACTED] mg	[REDACTED]	[REDACTED]
BMS-986288 + [REDACTED]	See note b	[REDACTED]	[REDACTED]
Nivolumab + [REDACTED]	See note b	[REDACTED]	[REDACTED]
Regorafenib Tablet	[REDACTED] mg c	[REDACTED]	Oral

Abbreviations: IV = intravenous; [REDACTED]

Note: Additional dose levels and/or administration schedules may be explored. BMS-986288 doses from [REDACTED] mg to [REDACTED] mg should be administered [REDACTED], BMS-986288 doses of [REDACTED] mg to [REDACTED] mg should be administered [REDACTED], and BMS-986288 doses of [REDACTED] mg to [REDACTED] mg should be administered [REDACTED]. The [REDACTED] of [REDACTED] mg of BMS-986288 in combination with [REDACTED] mg of nivolumab should be administered [REDACTED]. For participants weighing < 40 kg, [REDACTED] will be limited to 80 mL.

a Potential additional dose levels of BMS-986288 ([REDACTED] mg and [REDACTED] mg) could be [REDACTED] with [REDACTED] mg of nivolumab

b Dose(s) for BMS-986288 alone (Arm A) or in combination with nivolumab (Arm B) for [REDACTED] will be selected based on preliminary data from Part 1A and Part 1B.  
[REDACTED]

c See dose modification of regorafenib ([Section 7.4.6](#)).

For Part 2C Arm D dosing, please refer to local product label and institutional guidelines for further details.

The recommended dose of regorafenib is █ mg (four 40-mg tablets) taken orally once daily for the first 21 days of each 28-day cycle. Continue treatment until disease progression, unacceptable toxicity, withdrawal of consent, or the study ends, whichever occurs first. The participant should take regorafenib at the same time each day. Swallow tablet as a whole with water after a low-fat meal that contains less than 600 calories and less than 30% fat. The participant should not take 2 doses of regorafenib on the same day to make up for a missed dose from the previous day. Any missed doses reported by the participant should be recorded in the participant's source documents and in the participant's diary.

Initiation of the next treatment cycle:

1. The next cycle will be initiated █ with regorafenib dosing.
2. If regorafenib dosing is delayed, the next cycle will start if at least 4 weeks have passed from the first dose in the current cycle to dosing re-initiation.
3. The next treatment cycle may be initiated within a ± 3-day window of scheduled dose due to scheduling conflict.

See [Table 2-2](#) for treatment related Schedule of Activities. Refer to the Pharmacy Manual for additional dose preparation details for BMS-986288, nivolumab, and █ (if applicable).

## 7.2 Method of Treatment Assignment

During the screening visit for all study parts, the investigative site will call into the enrollment option of the IRT designated by BMS for assignment of a 5-digit participant number that will be unique across all sites. Enrolled participants, including those not dosed, will be assigned sequential participant numbers starting with █. The participant identification number (PID) will ultimately be comprised of the site number and participant number. For example, the first participant screened (ie, enrolled) at site number 1, will have a PID of █. Specific instructions for using the IRT system will be provided to the investigational sites in a separate document.

Participants will not be replaced if they are discontinued from the study secondary to an AE unless the AE can be determined to be unrelated to treatment.

During dose escalation, all participants will be assigned to Part 1A until the decision is made to escalate to the third dose cohort. Subsequently, treatment in Part 1B will be initiated, and dose escalation in the 2 parts will occur in parallel. █ will be initiated once an appropriate BMS-986288 monotherapy or combination dose is identified, will be incorporated through a protocol amendment, and may run in parallel with Part 1A and Part 1B. Treatment assignments for participants eligible for Part 1A, Part 1B, or █ will alternate between the 3 parts (if open), with consecutively treated participants assigned to different parts through IRT whenever possible according to the corresponding inclusion criteria. If there are no openings available in the part to which the participant would be assigned by this algorithm, then the participant will be

assigned to the next open part/cohort. Prioritization of participants eligible for both Part 1A and Part 1B may be modified to ensure the dose of BMS-986288 in the Safety Evaluation of BMS-986288 in Combination with Nivolumab (Part 1B) does not exceed the highest dose evaluated in the BMS-986288 Monotherapy Dose Escalation (Part 1A).

In Part 2A and Part 2B Combination Expansion, multiple doses may be open concurrently. In that case, treatment assignments will alternate between the dose levels, with consecutively treated participants assigned to different parts through IRT whenever possible. If there are no openings available in the dose level to which the participant would be assigned by this algorithm, then the subject will be assigned to the next open dose. Study treatment will be dispensed at the study visits as listed in the Schedule of Activities ([Section 2](#)) or [Appendix 8](#) (if applicable).

## **Part 2C**

Part 2C is a randomized, open-label study with 2 treatment arms, nivolumab in combination with BMS-986288 (Arm C) versus regorafenib (Arm D). Once enrolled in IRT, participants who have met all eligibility criteria for Part 2C will be randomized in a 2:1 ratio to nivolumab in combination with BMS-986288 (Arm C) or regorafenib (Arm D) and stratified by liver metastases status. Participants in Part 2C Arm D receiving regorafenib will have the option to transition to BMS-986288 in combination with nivolumab (Part 2C Arm Z) after BICR-assessed progression.

An additional dose of BMS-986288 █ mg or █ mg) in combination with nivolumab may be opened in Part 2C (as Arm E). This additional dose level will not be randomized with Arm C and Arm D.

### **7.3 Blinding**

This is an open-label study (open to sponsor and site/participant; not treated as sponsor-blind); however, the specific treatment to be taken by a participant will be assigned using an IRT. The site will contact the IRT prior to the start of study treatment administration for each participant. The site will record the treatment assignment on the applicable case report form, if required. Designated staff of BMS can have access to treatment assignments prior to database lock to facilitate data analysis, as well as the bioanalytical analysis of PK and immunogenicity samples. See [Section 10.3.8](#) for details of interim analysis. A bioanalytical scientist in the Bioanalytical Sciences department of BMS Research & Development (or a designee in the external central bioanalytical laboratory) and/or Clinical Pharmacology groups may obtain the treatment assignments in order to minimize unnecessary bioanalytical analysis of samples. This access to the treatment codes will not impact the data integrity of the study.

### **7.4 Dosage Modification**

[figure not shown]
Intra-participant dose escalation/reduction of BMS-986288 or nivolumab is not permitted in this study in order to allow better evaluation of the safety and efficacy at individual dose levels and schedules. Regorafenib starting dose modification can be considered in consultation with BMS Medical Monitor/designee. For AEs that are deemed to be related to regorafenib by the investigator, refer to local product label and institution guidelines for further detail in addition to the recommendation provided in [Section 7.4.6](#).

#### **7.4.1 Dose-limiting Toxicities**

For the purpose of guiding dose escalation, all AEs will be assessed and DLTs will be defined based on the incidence, intensity, and duration of the AEs for which no clear alternative cause is identified. The DLT period will be 5 weeks (35 days) in both BMS-986288 monotherapy and combination dose escalation (Part 1A and Part 1B). Any toxicities that occur beyond the DLT period will be accounted for in making final dose level decisions. Participants who have discontinued due to a DLT or who have received 2 doses of BMS-986288 monotherapy or in combination with nivolumab and have completed the 5-week DLT period will be considered as DLT-evaluable participants. Participants who withdraw from the study during the DLT evaluation period or have received less than 2 doses for reasons other than a DLT in both monotherapy and combination therapy will not be considered as DLT-evaluable participants and may be replaced with a new participant at the same dose level. Participants who are dose delayed during the DLT evaluation period for reasons other than a DLT in both monotherapy and combination therapy will be considered as DLT-evaluable participants if they received at least 2 doses of therapy within 8 weeks.

For the purpose of participant management, any drug related AE that meets DLT criteria, regardless of the cycle or cohort in which it occurs, will lead to discontinuation of study treatment.

AEs will be graded according to the NCI CTCAE v5.0.

Continuous evaluation of toxicity events in the [REDACTED] Evaluation of BMS-986288 [REDACTED] and BMS-986288 Cohort Expansion Combination Therapy (Part 2) will be performed. If at any time, the aggregate rate of treatment-related toxicities meeting DLT criteria in a BMS-986288 containing cohort exceeds 33% across patients treated in a cohort, the findings will be discussed with the Investigators and further enrollment may be interrupted. If a cohort is discontinued due to toxicity, a new cohort at a previously tested alternative dose level which was found to be safe in Part 1A or Part 1B may be considered based on the aggregate safety experience and in consultation and agreement between Investigators and Sponsor. An alternative dose or administration schedule may also be initiated in a specific [REDACTED] or Part 2 cohort upon

assessment of available safety, PK, pharmacodynamics, and efficacy data from that cohort. A protocol amendment reflecting any such new cohort will be submitted prior to enrollment to the cohort.

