Prior to declaring the MTD, and in consultation with investigators, the Sponsor has the option to expand any dose level previously established to be tolerable (during the DLT evaluation) in order to obtain additional experience or to investigate dose levels intermediate to those defined in the protocol (hereon referred to as “backfill”). The Sponsor may choose to enroll only participants with certain cancer types and certain criteria, from dose escalation during backfill, based on emerging data. Planned dose levels may be modified (eg, alternative administration schedule, [Appendix 8](#)), or intermediate dose levels added, based upon the BLRM analysis and clinical evaluation of available safety, PK, and pharmacodynamic data in Part 1A and Part 1B. Dose escalation in the alternative schedule may be performed; cohort tolerability assessment and subsequent dose recommendation will follow the same principles as outlined for the planned administration schedule of [REDACTED].

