## **APPENDIX 8      SCHEDULE OF ACTIVITIES, PHARMACOKINETICS SAMPLING SCHEDULE, AND BIOMARKER SAMPLING SCHEDULE FOR POTENTIAL ALTERNATIVE DOSE SCHEDULES IN CA043001**

Detailed in the tables below are the on-treatment schedule of activities, pharmacokinetic (PK) sampling schedule, and biomarker sampling schedule for potential alternative [REDACTED] BMS-986288 dosing administration that may be explored in CA043001 following evaluation of preliminary safety, PK, and pharmacodynamic data from [REDACTED] administration (Section 2). Decisions to initiate exploration of these alternative dose schedules will be made after discussion and agreement between the Investigators and the BMS Medical Monitor (or designee). If a cohort with a more frequent schedule of administration is explored, the dose level will be based on the PK data obtained from the [REDACTED] dosing schedule, and will not exceed a dose equivalent determined to be tolerable. Implementation of these alternative dose schedules will not include the addition of new procedures and will be documented in a note to file or administrative letter.

- [Table 1](#): On-treatment Schedule of Activities for BMS-986288 Monotherapy Q3W Dosing Schedule in CA043001
- [Table 2](#): PK and ADA Sampling Schedule for BMS-986288 IV Q3W Monotherapy in Dose Escalation (Part 1A) and BMS-986288 IV Q3W [REDACTED] Cohort Expansion (Part 2A)
- [Table 3](#): Biomarker Sampling Schedule for BMS-986288 Monotherapy Q3W Dosing Schedule in CA043001
- [Table 4](#): On-treatment Schedule of Activities for [REDACTED] Dosing Schedule for All Study Parts in CA043001
- [Table 5](#): PK and ADA Sampling Schedule for BMS-986288 IV [REDACTED] [REDACTED] (Part 1A and Part 2A)
- [Table 6](#): PK and ADA Sampling Schedule for BMS-986288 IV [REDACTED] in Combination with Nivolumab IV [REDACTED] (Part 1B and Part 2B)
- [Table 7](#): Biomarker Sampling Schedule for [REDACTED] Dosing Schedule for All Study Parts in CA043001

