**Table 4: On-treatment Schedule of Activities for [REDACTED] Dosing Schedule for All Study Parts in CA043001**

Procedure	Cycle 1 [REDACTED] days in length)				Cycle 2 [REDACTED] days in length)				Cycles 3 and Beyond (each cycle [REDACTED] days in length)		EOT a,b	Notes	
	D1	(± 2 days)	(± 2 days)	(± 2 days)	(± 2 days)	(± 2 days)	(± 2 days)	(± 2 days)	D1 (± 2 days)				
											protocol and Table 7 in Appendix 8 .		
Clinical Treatment Supplies													
BMS-986288 Administration [REDACTED]	X								X (Every other cycle starting at Cycle 3 [eg, C3, C5, C7, etc])		BMS-986288 to be supplied by BMS.		
Nivolumab Administration [REDACTED] (Part 1B, [REDACTED] Arm B, Part 2B)	X				X				X		Nivolumab to be supplied by BMS.		
Clinical Outcomes Assessments (Part 2 Only)													
NSCLC-SAQ	X				X				X	X			

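### On the optional every-other-cycle schedule, the two-dose rule for DLT-evaluability delays or drops DLT-free participants and biases the observed DLT rate upward

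*Combined protocol and SAP*

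**What the plan says.** Section 7.4.1 sets a DLT period of 5 weeks (35 days) for both Part 1A and Part 1B. A participant is DLT-evaluable by one of two main routes: they discontinued because of a DLT, or they "have received 2 doses of BMS-986288 monotherapy or in combination with nivolumab and have completed the 5-week DLT period". Those who "have received less than 2 doses for reasons other than a DLT" are not evaluable and may be replaced. A separate sentence covers participants whose dosing was delayed during the DLT period for a non-DLT reason; they count "if they received at least 2 doses of therapy within 8 weeks".

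Appendix 8 Table 4 describes an optional schedule on which BMS-986288 is given at Cycle 1 and then "Every other cycle starting at Cycle 3". Nivolumab, where used, is given every cycle.

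Section 5.1.2.1 allows dose escalation on an alternative schedule and says that "cohort tolerability assessment and subsequent dose recommendation will follow the same principles as outlined for the planned administration schedule of" a regimen whose name is blacked out. The same section places the cohort decision at the point where enough evaluable participants have completed the 5-week period. Appendix 8 adds that implementing an alternative schedule "will be documented in a note to file or administrative letter". Nothing in these sections adapts the two-dose condition or the 35-day window to the every-other-cycle schedule.

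**The concern.** The evaluability rule fits a schedule on which the second BMS-986288 dose falls inside the 35-day window. On the every-other-cycle schedule it falls well outside. Participants with and without a DLT are then judged over different periods: a DLT makes a participant evaluable at once, whereas a DLT-free participant must still be on treatment about three weeks after the window has closed.

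The DLT count among evaluable participants is the input to the dose-escalation model. Sections 10.1.1 and 10.1.2 target a DLT rate between 16% and 33% and cap at 35% the posterior probability that the rate reaches 33% or more. Selectively removing DLT-free participants pushes the observed rate in one direction, towards that boundary. It also leaves the 5-week decision point with no DLT-free monotherapy data, and it invites replacement of participants who were in fact observed for the full window.

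The mismatch could pass unnoticed, because the schedule may be opened without a protocol amendment. The amendment requirement at the end of Section 7.4.1 concerns new cohorts in Part 2 and in the evaluation whose name is blacked out. It does not clearly reach Part 1 escalation.

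**Working it through.** **Inputs**
- DLT period: 5 × 7 = 35 days (Section 7.4.1).
- Dose-delay allowance: 8 × 7 = 56 days (Section 7.4.1).
- BMS-986288 dosing days on the alternative schedule: C1D1, C3D1, C5D1 (Appendix 8 Table 4, including its vital-signs footnote).
- Cycle length: blacked out, but Appendix 8 Table 5 places C2D1 at 672 hours after the C1D1 infusion, and 672 / 24 = 28 days. I assume Cycle 2 has the same length.
- Visit window: ± 2 days (Section 5.1.2.4 and Table 4).

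**When the second dose falls**
- C3D1 = 2 × 28 = 56 days after the first dose, that is Day 57 (Day 55 to Day 59 with the visit window).
- 57 − 35 = 22 days after the window closes. By Day 35 only one BMS-986288 dose has been scheduled.
- This does not depend on Cycle 2 being exactly 28 days. Appendix 8 Table 7 schedules a C2D22 visit, which is Day 28 + 22 = 50, so C3D1 lies beyond Day 50 in any case.

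**Comparison with other schedules**
- Q3W alternative: second dose on Day 22, inside the window.
- Planned schedule: cycle length blacked out. If it is 28 days, the second dose is on Day 29, inside the window.
- Part 2 monitoring: Section 10.3.8.1 counts all treated participants, so the rule does not apply.

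**The 8-week sentence.** It is written for participants whose dosing was delayed, and someone dosed on schedule is not delayed. If it were applied anyway, an on-time second dose at 56 days sits exactly on the 56-day limit, and a permitted visit 1 or 2 days late (57 or 58 days) misses it.

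**Effect under the literal reading** (two doses at any time, plus 35 days completed). Let p be the true DLT rate and d the share of DLT-free participants who complete 35 days but leave treatment before C3D1. Then

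observed rate = p / [p + (1 − p)(1 − d)]

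- p = 0.16, d = 0.10: 0.16 / (0.16 + 0.756) = 17.5%
- p = 0.16, d = 0.40: 0.16 / (0.16 + 0.504) = 24.1%
- p = 0.33, d = 0.10: 0.33 / (0.33 + 0.603) = 35.4%
- p = 0.33, d = 0.40: 0.33 / (0.33 + 0.402) = 45.1%

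The range for d is my assumption; the documents give no attrition figure. In a cohort of six with one DLT, the count is 1/6 (17%) if all five others reach C3D1, 1/5 (20%) if one leaves, and 1/4 (25%) if two leave.

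**Effect under a within-window reading** (both doses required by Day 35). The DLT-free evaluable share is zero, so the observed rate is 100% whatever p is, and 1/6 becomes 1/1. The chance that none of three treated participants is evaluable is (1 − p)³, which is 0.84³ = 59% at p = 0.16 and 0.67³ = 30% at p = 0.33.

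**The case against.** A reader might infer that the rule can never be met on this schedule, so that every evaluable participant has a DLT, the model sees a 100% rate and a DLT-free cohort never becomes evaluable. The documents do not support that as the plain meaning. Section 7.4.1 joins two conditions, two doses received and the 5-week period completed, and does not say that both doses must fall within the 35 days. A DLT-free participant dosed at C3D1 satisfies both. The 8-week sentence shows that the section accepts a second dose after Day 35 in at least one situation. That sentence also gives some support to the within-window reading, since it would have little purpose if two doses at any time were enough, but the text does not settle the matter.

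Other points on the plan's side:
- Section 10.1.1 says the model draws on all dose levels and on ipilimumab experience, and that clinical assessment considers all treated participants. This softens the effect of a distorted count in one cohort but does not correct the count.
- Replacement is permitted, not required. That stands.
- In Part 1B nivolumab is given every cycle, and the 8-week sentence counts doses of therapy, so the combination count is ambiguous. The main rule names BMS-986288, and monotherapy has no such way out.
- The schedule opens only after the Investigators and the Medical Monitor agree, and carrying over the same principles need not mean carrying over every numerical criterion. Both are fair, but neither tells the team which rule to use instead.

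**Conclusion.** The mismatch holds, within limits. At the 5-week decision point on the every-other-cycle schedule, no DLT-free monotherapy participant is yet evaluable; for Part 1B the position is ambiguous. On the literal reading, evaluability comes at about Day 57 and requires staying on treatment until then. The decision is delayed by about three weeks and the observed DLT rate is biased upward, by 1.5 to 8.1 percentage points at a true 16% and by 2.4 to 12.1 points at a true 33%. The 100% result follows only if both doses are read as required within the window.

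These sizes rest on the assumed 10% to 40% loss between Day 35 and Day 57, on 28-day cycles, and on every DLT in the window being counted. The direction of the bias does not depend on the size of the loss, provided some DLT-free participants leave. The scope is Part 1 escalation on one optional schedule; the Q3W alternative and Part 2 are unaffected. It should be resolved before that schedule is opened.

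**What to change.** Reconcile Sections 5.1.2.1 and 7.4.1 with Appendix 8 Table 4 before the every-other-cycle schedule is used. In Section 7.4.1, define a DLT-free participant as evaluable when they have completed the DLT period and received the BMS-986288 doses (and, where applicable, the nivolumab doses) scheduled within that period for the schedule in use. Keep the existing route for those who discontinued because of a DLT, and keep the 8-week sentence for delayed dosing. Participants with and without a DLT are then judged over the same observation period.

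This wording would make one BMS-986288 dose sufficient on the every-other-cycle schedule if the window stays at 35 days. The documents do not make that choice, so the sponsor should state which window and exposure apply to that schedule, and whether nivolumab doses count in Part 1B. Appendix 8 should refer back to the revised definition.

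The cost is a sentence or two in Section 7.4.1 and a cross-reference, with no added participants or assessments unless the sponsor chooses a longer window. Where two doses already fall within 35 days, the definition does not change.
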